9.0 SPONSOR RESPONSIBILITIES

9.1 Role of Interscope

As the study Sponsor, Interscope, Inc. is responsible for the overall conduct and quality of the study, including the assurance that the study complies with the appropriate standards and regulations that apply to medical device clinical investigations. Interscope will also ensure adherence to the Sponsor general duties as outlined by GCP standards and the US FDA standards. Additionally, the Interscope study management will ensure that qualified monitors are monitoring the study according to the protocol, GCP standards and study regulations, and that the Informed Consent process is followed per each site's local and US FDA requirements.

9.2 General Duties (21 CFR 812. 40)

Interscope general duties, either directly or as delegated to its CRO, consist of submitting the IDE application to FDA and obtaining FDA approval for the IDE prior to shipping devices, selecting qualified investigators and clinical sites, ensuring that each site has obtained IRB approval prior to shipping devices to that site, ensuring proper clinical site monitoring and GCP compliance, and ensuring that informed consent is obtained for each enrolled patient.

Interscope will also ensure adherence to the FDA regulations and the Sponsor general duties (21 CFR 812.40), selection of investigators (21 CFR 812.43), monitoring (21 CFR 812.46), supplemental applications [21 CFR 812.35 (a) and (b)], maintaining records [21 CFR 812.140 (b)], and submitting reports [21 CFR 812.150 (b)].

Interscope will collect quality data that satisfies federal regulations including serious unanticipated adverse events and deviations from the protocol. Interscope will prepare written progress reports and a final study report at the completion of the study.

9.3 Selection of Clinical Sites & Investigators

Interscope will select qualified clinical sites and Investigators who are experienced with endoscopic resection and ablation devices. The Investigator must work with a qualified IRB to oversee the rights, safety and welfare of the study participants. The clinical site must also have an adequate patient population and the appropriate staffing and equipment to meet the requirements of the study protocol and the expected enrollment timeframes. All sites will be pre-qualified by the Sponsor or its CRO. Financial disclosures will be collected from all investigators during the site qualification process.

Interscope will ship devices only to participating investigators, obtain a signed Investigator's Agreement and provide the investigators with the information necessary to conduct the study.

9.4 Investigator & Staff Training

Training of the Investigators and clinical study staff is the responsibility of the Sponsor, Chief Medical Officer, designated monitors and/or the CRO. Training may be conducted during an Investigator meeting, a site initiation visit, or appropriate training venues. Investigators and study staff will undergo training on the study devices and study protocol prior to participating in the study. Training may encompass didactic information regarding the study devices as well as hands-on practice. Procedural technique and experience with the Interscope device will be assessed by the Trainer during the first case at each site. Observations during the

cases will also be discussed with the Investigator and study staff. Study and support staff at the clinical site will also be trained on the study protocol, eligibility criteria, the Instructions for Use, and proper storage of the device and supplies.

9.5 Monitoring

The Sponsor and/or the CRO will monitor the study and will select or designate clinical monitors who are qualified by training and experience, to monitor and oversee the conduct of the ENDOROTOR study. The clinical monitors will follow the Sponsor's standard operating procedure for monitoring and the Monitoring Plan to be written on a risk-based approach for this study. The Monitoring Plan will require evaluation of compliance with the protocol, GCP compliance, FDA regulations, and any specific recommendations made by the site's IRB and the signed Investigator and Study Agreements. Periodic phone contacts, site visits, and intermittent remote visits will be conducted to ensure that the protocol is being followed. The clinical monitor(s) will also verify that the Case Report Forms (CRFs) are in agreement with the source documentation and other records.

On-site and intermittent remote monitoring of all study sites will be frequent enough to ensure continued acceptability of the data by assessing compliance of the site to the Investigational Plan, adherence to the data collection procedures, and maintenance of study records. If necessary, appropriate corrective action will be taken to ensure adherence to the study protocol.

For record verification purposes, the monitor and/or authorized Sponsor representative will be provided access to hospital records, original laboratory data, and other records and data as they relate to the study and as agreed to with the Investigator prior to the initiation of the trial. The Investigator will also make available to the clinical monitor all regulatory documents, all completed CRFs, informed consent documents, source documentation and other relevant records for all enrolled subjects at the site. It is important that the Investigator and other relevant site personnel are available for consultation with the clinical monitors during the monitoring visits and that sufficient time is devoted at the site to the monitoring process.

If the Sponsor and/or their authorized representatives becomes aware that an Investigator is not complying with the study protocol, the Investigator Agreement, the Declaration of Helsinki, GCP standards, applicable privacy standards, or any condition of the study imposed by the IRB or the FDA, the Sponsor or their authorized representatives will immediately secure compliance or discontinue further shipments of the study devices. An inability to secure compliance and/or to complete an investigation into the factors that are inhibiting compliance may result in the Investigators termination from the study by the Sponsor.

Study close-out visits will be conducted after the final follow-up visit is completed at each site. Following the resolution of any outstanding data discrepancies and adverse events, the remaining investigational study devices will be collected and returned to the Sponsor. A final study report will be generated and submitted to the Investigator and the appropriate study oversight authorities. Study document retention requirements will be reviewed with each site during the close-out visit.

9.6 On-Site Audits

In accordance with GCP and US FDA requirements, a Sponsor or CRO representative may request access to all study records, including source documents, for inspection and duplication. In the event that an Investigator is contacted by a regulatory agency or local IRB in relation to this study, the Investigator will notify the Sponsor or designated monitor/CRO as soon as possible.

The Investigator and/or designees must be available to respond to reasonable requests by authorized Sponsor, CRO and regulatory agency representatives during the monitoring and inspection process. The Investigator must provide the Sponsor and CRO with copies of all correspondence that may affect the review of the current study (i.e. Inspection Observations) or their qualification as an Investigator in clinical studies conducted by the Sponsor. The Sponsor will provide any needed assistance to the clinical site for regulatory audits.

9.7 Records & Record Retention

The Sponsor and/or designated monitor/CRO will maintain copies of correspondence, Investigator Agreements, clinical data, device shipments, clinical events (AEs, SAEs, and UAEs), adverse device effects and other records related to the clinical trial and supporting documentation, and other records and reports related to this clinical study.

The Sponsor, core Laboratories and clinical sites will maintain the study records until 2 years after the final study report is completed, or longer if required by local or national regulatory agencies. The Sponsor and/or CRO will notify each site regarding the regulatory requirements for record retention during the study close-out visit.

9.8 Sponsor Reports

Interscope, Inc. will submit the required FDA reports identified in 21 CFR 812.150 (B). This includes unanticipated adverse device effects, withdrawal of IRB or FDA approval, current Investigator list (every 6 months), annual progress reports, recall information, final reports and protocol violations.

9.8.1 Study Data Reports

All information and data generated in association with the study will be held in strict confidence and remains the sole property of the Sponsor. The Investigator agrees to use this information for the sole purpose of completing the study and for no other purpose without prior approval of the Sponsor.

Upon receipt of the final study data and the final reports from each center, the Sponsor will complete a final study report. Copies of the final report will be provided to each Investigator.

9.9 Supplemental Applications

As appropriate, the Sponsor will submit changes to the study protocol to the FDA and to the Investigators to obtain IRB re-approval.

9.10 Coverage of Patient Expenses

The treated subjects will not be compensated for their time during the trial. The Sponsor may provide reimbursement for modest out-of-pocket patient costs associated with travel, parking, or other expenses associated strictly with completing the protocol requirements of this study that would not normally be covered under routine medical coverage for the patient's underlying medical condition if such reimbursement is approved in writing by the local IRB prior to study enrollment.

10.0 QUALITY ASSURANCE & ETHICAL STANDARDS

The study will be conducted according to the Declaration of Helsinki, Good Clinical Practice Guidelines (GCP), US FDA regulations, and any additional IRB requirements that apply to clinical investigations of medical devices. As the study Sponsor, Interscope has the overall responsibility for the conduct of the study, including

the assurance that the study is in compliance with these guidelines, standards and requirements.

10.1 Medical Monitor

To meet the ethical responsibilities and standards for research subjects, the Medical Monitor (Sponsor's Chief Medical Officer) will review all adverse events, serious adverse events, unanticipated adverse device effects, and in conjunction with the engineering department any device performance report, failure or malfunction that could potentially impact the treatment of, or the clinical outcomes of subjects enrolled in the study. In the event that further investigation is required for any significant clinical or device performance issue that is identified in the trial the Medical Monitor or Sponsor's Regulatory Representative will initiate a corrective and preventative action (CAPA) procedure within the Interscope Quality Management System to further investigate and resolve the occurrence.

10.2 Safety Monitoring & Study Termination

The Medical Monitor will closely monitor current medical practice, device performance, and the occurrence of and rate of occurrence of adverse events, serious adverse events, and unanticipated adverse device effects to determine if there is an unreasonable risk to the study participants. If warranted, the study protocol may be amended, and/or the study may be suspended or terminated early.

An independent Data Monitoring Committee (DMC) consisting of at least three members will review serious adverse events and safety endpoint events. Adjudication of adverse events will be conducted according to a Data Monitoring Committee Charter to be approved by the Sponsor and the DMC. The Charter will include:

- Stopping rules
- Planned Safety Reviews: Safety reviews will occur at predetermined intervals
- Unplanned Safety Reviews: Any safety concerns that arise during the trial will be brought to the attention of the IPA. A full DMC meeting can be called at the discretion of the DMC Chairperson. The DMC Chairperson may also request additional data reviews when considered necessary to monitor the progress of the trial.
- DMC reports are to include:
 - Rates of recruitment, ineligibility, noncompliance, protocol violations and dropouts, overall and by study site;
 - Completeness and timeliness of data;
 - Duration of follow-up and early study discontinuation;
 - Baseline characteristics and demographics;
 - Medical History;
 - Device data;
 - Adverse Events;
 - Serious Adverse Events; and
 - Unanticipated Adverse Device Effects
 - A significant difference in safety or effectiveness between the EndoRotor and the control devices
 - Decision on continuing or stopping the study based on safety and effectiveness of the study device and the control devices

The DMC will be determined prior to the study and records of event review will be documented and maintained in the study records. The DMC will be completely independent of the Sponsor and the ENDOROTOR study. The Sponsor may terminate Investigator and site participation in the study if there is evidence of an Investigator's failure to maintain adequate clinical standards or evidence of continued serious protocol deviations.

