7.0 STATISTICAL METHODS

7.1 General Principles

By-subject listings will be created for each CRF module. Summary tables for continuous variables will contain the following statistics: N, mean, median, standard deviation, minimum, maximum, and 95% confidence interval (CI) as appropriate. Summary tables for categorical variables will include N, percentage, and 95% CIs on the percentage. CIs for proportions will be calculated using the Clopper- Pearson exact method. Graphical techniques will be used when such methods are appropriate and informative. Tables will separate data by treatment arm.

Transformations of the data may be explored if warranted by the distribution of the data. Analyses resulting from transformations applied after the data are unmasked will be considered to be exploratory.

Unless otherwise specified, all analyses will be 2-sided at the 0.05 level of significance. All analyses will be performed using SAS® (Version 9.4) and graphs using R, version 3.3.1 or later, or using SAS®.

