7.8 Statistical Analysis of Primary and Secondary Effectiveness Endpoints

In testing for non-inferiority of the primary effectiveness, a two-tailed 95% confidence interval (CI) for the difference in two rates will be used to examine the location of the lower boundary of the CI relative to the 10% NI delta. An NI delta of 10% is judged to be clinically acceptable for this indication. Further, given an expected 30% advantage of the test device over the active control (80% vs 50%), by setting the non-inferiority margin at 10%, we are retaining 67% of the active treatment advantage as opposed to a using a

more standard value of 50% (Non-Inferiority Clinical Trials to Establish Effectiveness Guidance for Industry, U.S. Department of Health and Human Services Food and Drug Administration Center for Drug Evaluation and Research (CDER) Center for Biologics Evaluation and Research (CBER) November 2016 Clinical/Medical).

In testing for superiority of the primary effectiveness endpoint, the same logistic regression model, used to test for NI will be evaluated. Alpha of 0.05 will be used to test for significance.

The secondary effectiveness endpoint will be tested with a Wilcoxon rank-sum test. An alpha of 0.05 will be used to test for significance.

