7.8.2 Interim Analysis

No interim analysis of effectiveness endpoints will be performed.

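### Section 10.2 gives the DMC an effectiveness comparison and a stop decision that section 7.8.2 rules out; the 5% error rate may not be protected, depending on the Charter

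*Combined protocol and SAP*

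**What the plan says.** Section 7.8.2 is a single sentence: "No interim analysis of effectiveness endpoints will be performed". The error budget matches it. Section 7.1 sets the default that "all analyses will be 2-sided at the 0.05 level of significance", and section 7.8 says of the final superiority test that "Alpha of 0.05 will be used to test for significance". Section 7.8.3 orders the tests (non-inferiority, then superiority, then the secondary endpoint) and says nothing about repeated looks.

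Section 10.2 starts from a safety remit: the DMC "will review serious adverse events and safety endpoint events". The timetable is worded the same way: "Planned Safety Reviews: Safety reviews will occur at predetermined intervals". Beyond the timetable, "The DMC Chairperson may also request additional data reviews when considered necessary to monitor the progress of the trial". The list of DMC report contents then ends with two items of a different kind: "A significant difference in safety or effectiveness between the EndoRotor and the control devices" and "Decision on continuing or stopping the study based on safety and effectiveness of the study device and the control devices".

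The Charter is to contain stopping rules and is still to be approved by the sponsor and the DMC. Its content is not in the documents.

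**The concern.** A DMC cannot report a significant difference in effectiveness between the arms unless someone has compared effectiveness between the arms before the end. Section 7.8.2 says nobody will. Section 10.2 then ties effectiveness to the decision to continue or stop, without limiting that decision to harm or lack of effect.

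The final test is at stake. If a DMC acting under section 10.2 stopped the trial because the device looked better, and the result were judged at an unadjusted 0.05, the chance of a false claim would exceed the stated level and the estimated benefit would tend to be too large. Nothing in sections 7.1, 7.8 or 7.8.3 reserves alpha for that. Section 4.5 calls this a pivotal study, so the meaning of its primary p-value should not depend on which of two sections the DMC follows.

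**Working it through.** **Inputs.** From section 7.3: response 80% on EndoRotor and 50% on control, 55 evaluable subjects per arm, superiority power 91.6% (section 4.7 rounds this to 90%). From sections 7.1 and 7.8: two-sided 0.05 at one final analysis. Not given anywhere: the number and timing of DMC looks at effectiveness, and any boundary. These are assumed below and varied.

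**Step 1: the plan's own power.** With d = 0.30, mean rate 0.65 and n = 55, the pooled-variance formula is

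Power = Φ{[d − z·√(2 × 0.65 × 0.35/n)] / √[(0.8 × 0.2 + 0.5 × 0.5)/n]}.

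- √(0.455/55) = 0.0910
- √(0.41/55) = 0.0863
- With z = 1.96: (0.30 − 0.1783)/0.0863 = 1.41, so power = 92.1%

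This is close to the stated 91.6%. The plan's power therefore assumes that all of the 0.05 is available at a single final test.

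**Step 2: type I error if the DMC may stop for benefit at nominal 0.05.** Under no difference, the statistic at look k of K equally spaced looks is Z_k = (X_1 + … + X_k)/√k, with independent standard normal X. The two-sided error is the chance that any |Z_k| exceeds 1.96. The device-favouring error is the chance that any Z_k exceeds 1.96. From 2 million simulated null paths:

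| Looks, including the final one | Two-sided (target 5%) | Favouring the device (target 2.5%) |
|---|---|---|
| 1 | 5.0% | 2.5% |
| 2 | 8.3% | 4.2% |
| 3 | 10.7% | 5.4% |
| 4 | 12.6% | 6.3% |

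For one interim look at information fraction t, the interim and final statistics are bivariate normal with correlation √t. The two-sided error is 1 − P(|Z_1| < 1.96 and |Z_2| < 1.96): 9.1% at t = 0.25, 8.3% at t = 0.5 and 7.3% at t = 0.75.

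**Step 3: other rules the Charter might contain.**

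- One look at half information, stopping only at two-sided p<0.001, with the final test left at 0.05: total two-sided error 5.02%.
- Stopping only for harm or lack of effect: no inflation, because such a stop can only remove chances to claim benefit.

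**Step 4: cost of a formal look.** For one look at half information (assumed), the O'Brien-Fleming boundary is c at the end and c√2 at the interim, with c = 1.977 so that the total two-sided error is 5%. The nominal two-sided levels are 0.0052 at the interim and 0.0480 at the end. Putting z = 1.977 into the formula of step 1 gives (0.30 − 0.1799)/0.0863 = 1.39, so power at the final level alone is 91.8%, against 92.1%.

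**Step 5: how many looks are plausible.** The protocol summary plans 12 months of enrolment, and no subject's outcome is complete before 6 months; some take 9 months, and Scenario 4 in section 5.7.1.4 takes 12. With uniform accrual (assumed), half the subjects are enrolled by month 6, and their outcomes are complete at month 6 + 6 = 12 at the earliest. Half information thus arrives at about the end of enrolment or later. Several early, evenly spaced looks are possible on paper but are not the natural case.

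**The case against.** The strongest reply is that section 10.2 concerns safety. Its title, the stated remit and the scheduled reviews all say so. No effectiveness endpoint, test, significance level, population or timing is given for the DMC. The word significant need not mean a p-value: sections 10.1 and 10.4 use it in a clinical sense. A decision that weighs effectiveness can be a benefit-risk judgement on descriptive data, which is compatible with section 7.8.2. The Charter's stopping rules may also set a strict boundary.

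Much of this stands. A reader might infer that every scheduled review is an unadjusted effectiveness look, that the plan allows stopping for benefit at 0.05, or that the error rate is simply 8% to 13%. The documents support none of these. The scheduled reviews are called safety reviews, no rule for stopping on benefit is stated, and the Charter is not available. The two-sided figures also count false results against the device, whereas the superiority hypothesis in section 7.6 is directional; the device-favouring figures are about half as large.

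The conflict itself remains. Effectiveness is named in both bullets, one of which speaks of a significant between-arm difference and the other of stopping. A Charter boundary for effectiveness would contradict section 7.8.2. A Charter without one would leave section 10.2 open to the reading in step 2.

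**Conclusion.** The point holds as a conflict between sections 7.8.2 and 10.2, with a conditional consequence: the 5% error rate may not be protected, depending on stopping rules that the documents do not show. Inflation needs two things together: the DMC must compare effectiveness in spite of section 7.8.2, and it must be able to stop for benefit at a loose threshold.

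The possible size therefore runs from no inflation (stops for harm or lack of effect only), through 5.02% (one strict look), to the figures of step 2 (nominal 0.05 at every look). The step 2 figures rest on an assumed number of looks, equal spacing and stops that are always acted on; they illustrate the exposure and do not estimate this trial's error rate. Should-fix: the repair is wording, and the specific statistical provision in section 7.8.2 is itself clear.

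**What to change.** In section 10.2:

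- Remove effectiveness from the bullet on a significant difference between the devices.
- State that effectiveness data go to the DMC only descriptively, as context for benefit and risk.
- State that the study will not be stopped early for benefit.
- Require the Charter to agree with section 7.8.2.

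Stopping for safety or for lack of effect need not be removed, since neither raises the type I error. Alpha stays at 0.05 and power is unchanged. The cost is an edit to the protocol and to a Charter that is still to be approved, plus giving up unplanned early stopping for benefit.

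If the sponsor wants the option of stopping for benefit, section 7.8.2 should instead pre-specify one look with its timing, an O'Brien-Fleming boundary and the matching final level. At half information, for example, the nominal two-sided levels are 0.0052 and 0.0480. Power at the final level is about 91.8% against 92.1%, so no material increase in sample size follows. By step 5, such a look would come at about the end of enrolment or later, so it would save few subjects.
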